4.1.5 Blinding and procedures for unblinding

4.1.5.1 Blinding

This phase I trial will be performed according to an open-label, single arm design. It will recruit patients with relapsed and/or refractory MM. This open-label trial will be handled in an open fashion by the sponsor throughout, i.e. also for the purpose of data cleaning and preparation of the analysis. The eCRF will contain information on the treatment and the dose.

4.1.5.2 Procedures for emergency unblinding

Not applicable.

4.1.6 Packaging, labelling, and re-supply

BI 836909 will be supplied in lyophilized vials containing 75µg BI 836909 to be reconstituted with 1ml water for injection (WFI). Water for injection will not be provided. One pack of medication contains 1 vial of lyophilized BI 836909 and 1 vial of 5 ml bag diluent. For details of packaging and the description of the label, refer to the ISF.

Medication will be delivered to the investigator's pharmacy where the total dose per patient will be prepared upon request from the investigator.

Re-supply will be managed by IWRS system.

Proprietary confidential information.

© 2018 Boehringer Ingelheim International GmbH or one or more of its affiliated companies. All rights reserved.

This document may not - in full or in part - be passed on, reproduced, published or otherwise used without prior written permission.

4.1.7 Storage conditions

BI 836909 which will be provided by the sponsor must be kept in a secure, limited access storage area under the storage conditions defined by the sponsor and at the temperature indicated on the trial drug label. BI 836909 as well as the bag diluent must be stored in a refrigerator at 2 – 8°C and should not be frozen. Drug supplies will be kept in their original packaging. A temperature log must be maintained for documentation.

If the storage conditions are found to be outside the specified range, immediately contact the local clinical monitor or the CRA as provided in the list of contacts. For more details on BI 836909, please refer to the IB ([c02942358](#)) and the ISF.

In-use stability of BI 836909 and Bag Diluent refers can be found in the "Instruction for Pharmacists". These will be provided within the ISF and pharmacy file.

4.1.8 Drug accountability

The pharmacist will receive the investigational drugs delivered by the sponsor when the following requirements are fulfilled:

- approval of the study protocol by the IRB / ethics committee,
- availability of a signed and dated clinical trial contract between the sponsor and the Head of the investigational site,
- approval/notification of the regulatory authority, e.g. competent authority,
- availability of the curriculum vitae of the principal investigator,
- availability of a signed and dated clinical trial protocol
- Reference ranges for local laboratory values.

The Investigator/pharmacist/investigational storage drug manager will receive the investigational drugs delivered by the sponsor after the IRB/ethics committee approval of the trial and completion of a clinical trial contact between the Sponsor and the Head of Trial Center.

The Investigator and/or pharmacist and/or investigational drug storage manager must maintain records of the product's delivery to the trial site, the inventory at the site, the use by each patient, and the alternative disposition of unused products.

These records will include dates of receipt, quantities, batch/serial numbers, expiry ('use by') dates, and the unique code numbers assigned to the investigational products and trial patients. The investigator/pharmacists/investigational drug storage manager will maintain records that document adequately that the patients were provided the doses specified by the CTP and reconcile all investigational products received from the sponsor. At the time of return to the sponsor and/or appointed CRO, the investigator/pharmacists/investigational drug storage manager must verify that all unused or partially used drug supplies have been returned by the patient or homecare service to the trial site and that no remaining supplies are in the investigator's possession.

Proprietary confidential information.

© 2018 Boehringer Ingelheim International GmbH or one or more of its affiliated companies. All rights reserved.

This document may not - in full or in part - be passed on, reproduced, published or otherwise used without prior written permission.

The Investigator/pharmacist/investigational storage drug manager will receive the investigational drugs delivered by the sponsor after the IRB/ethics committee approval of the trial and completion of a clinical trial contact between the Sponsor and the Head of Trial Center.

4.2 CONCOMITANT THERAPY, RESTRICTIONS, AND RESCUE TREATMENT

4.2.1 Rescue medication, emergency procedures, and additional treatment(s)

4.2.1.1 Rescue medication

Rescue medication in term of an antidote to reverse the action of BI 836909 is not available. Potential side effects of BI 836909 have to be treated symptomatically.

All concomitant or rescue treatment(s) taken during the course of the trial must be recorded in the source documents (e.g. patient files) and in eCRF.

4.2.1.2 Supportive care

Patients should receive supportive care according to local guidelines regarding treatment of infusion-related reactions ([Section 4.1.4.1.2](#)), blood product support, antibiotics, antivirals, analgesics, etc. In the case of a tumour lysis syndrome, supportive therapy including rasburicase may be used as clinically indicated at the investigator's discretion.

4.2.1.2.1 Treatment of Myeloma Bone Disease, Hypercalcemia, Pain and Renal Failure

Treatment of myeloma bone disease, hypercalcemia, pain and renal failure should be done according to institutional standards.

4.2.1.2.2 Growth factors

The use of growth factors such as Erythropoiesis-Stimulating Proteins as well as granulocyte colony stimulating factor (G-CSF) will be allowed during therapy. However, growth factors are not allowed at inclusion and should be avoided, if patient's condition allows, in the first treatment course for better assessment of safety parameters.

4.2.1.2.3 Infections

Prophylactic antibiotics, antifungal and antivirals are allowed and should be given according to institutional standards. Pneumocystis prophylaxis should also be given according to institutional standards. For patients who are considered to have an increased risk for herpes infections, the prophylaxis is mandatory unless medically contraindicated. Subjects who may experience neutropenia for 7 days or longer are at a high risk for infectious complications. As appropriate, these subjects will be administered prophylactic antibacterial, antifungal, and antiviral medications. These subjects will be monitored for early signs of breakthrough infections after the initiation of antibacterial therapy to prompt additional evaluation and possible therapy modification.

Proprietary confidential information.

© 2018 Boehringer Ingelheim International GmbH or one or more of its affiliated companies. All rights reserved.

This document may not - in full or in part - be passed on, reproduced, published or otherwise used without prior written permission.

Patients who develop fever $>38.3^{\circ}\text{C}$ or a sustained temperature of $>38^{\circ}\text{C} \geq 1 \text{ h}$ will be hospitalised, undergo the following diagnostic work-up and started on empirical treatment with broad spectrum i.v. antibiotics according to institutional standards:

- Blood cultures from central line and peripheral veins
- Urine culture
- CT-Thorax low dose
- Respiratory virus by pharyngeal wash (Parainfluenza 1-4, Influenza A + B, Adenovirus, Metapneumovirus, Echovirus, Rhinovirus, Bocavirus, Coronavirus, Entrovirus und RSV by multiplex PCR)

Subjects with active systemic infections requiring IV antibiotics, antivirals, or antifungals should not be dosed with BI 836909 until infection has resolved and if being treated with an anti-infectious therapy, the course of such therapy should have been completed.

Patients requiring interruption of treatment for >14 days due to active infection will be permanently discontinued.

4.2.1.3 Concomitant medication

All concomitant therapies to provide adequate care may be given as clinically necessary, unless given as anti-myeloma therapy. Bis-phosphonates can be given as clinically indicated. All concomitant treatments should be recorded in the eCRF except for vitamins or nutrient supplements. Trade names, indication and dates of administration of concomitant therapies will be documented. For parenteral nutrition during the trial, the components not need to be specified in detail. It should just be indicated as “parenteral nutrition”. If a patient needs general anaesthesia, it will be sufficient to indicate “general anaesthesia” without specifying the details.

Concomitant therapy should be recorded in the eCRF during the screening and treatment period, starting at the date of signature of informed consent, and ending at the EOT visit. After EOT visit, only concomitant therapy indicated for treatment of an adverse event has to be reported or if given as anti-myeloma therapy.

4.2.2 Restrictions

4.2.2.1 Restrictions regarding concomitant treatment

Previous therapies for multiple myeloma must have been discontinued at least two weeks before the first administration of trial drug (see exclusion criteria [Section 3.3.3](#) for details) and patient must have recovered from all clinically relevant toxicities. A time interval of at least four weeks must have elapsed from the last administration of any other investigational treatment for multiple myeloma to the first administration of BI 836909.

No anti-neoplastic therapy concomitantly is allowed.

No other investigational therapy concomitantly is allowed.

Proprietary confidential information.

© 2018 Boehringer Ingelheim International GmbH or one or more of its affiliated companies. All rights reserved.

This document may not - in full or in part - be passed on, reproduced, published or otherwise used without prior written permission.

Additional glucocorticoid medications may be used as clinically indicated to treat infusion-related reactions at any dose. Short term systemic glucocorticoid for lung disease (for example asthma or COPD) may be used. Daily oral steroid treatment may be administered at doses equivalent to prednisolone 10 mg per day. All other indications for steroids have to be discussed and agreed upon between investigator and sponsor.

4.2.2.2 Restrictions on diet and life style

No restrictions apply with regards to diet or life style unless based on restrictions due to the portable pump used within the study.

4.3 TREATMENT COMPLIANCE

BI 836909 will be administered as a continuous intravenous infusion (c.i.v.) via infusion pump over a period of 4 weeks. Infusion bags will have to be exchanged approximately every 4 days either at site or by a trained care provider. Persons involved in exchange of the bag will document compliance. Compliance may also be verified by pharmacokinetic assessments. Any discrepancies will be explained in the eCRF by the investigator or his/her deputy.

Proprietary confidential information.

© 2018 Boehringer Ingelheim International GmbH or one or more of its affiliated companies. All rights reserved.

This document may not - in full or in part - be passed on, reproduced, published or otherwise used without prior written permission.

5. VARIABLES AND THEIR ASSESSMENT

5.1 EFFICACY - CLINICAL PHARMACOLOGY OR PHARMACODYNAMICS

5.1.1 Endpoint(s) of efficacy

The efficacy endpoints will be assessed at the time points specified in the [flowcharts](#). Efficacy endpoints will be secondary or further endpoints in the trial and will be evaluated according to the response criteria of the International Myeloma Working Group (IMWG, 2006; [Appendix 10.1](#)).

Secondary endpoints of efficacy are:

- Objective response rate (percentage of patients with stringent complete response (sCR), complete response (CR), partial response (PR) and very good partial response (VGPR))
- Duration of response (DOR)
- Minimal residual disease (MRD) response rate
- Duration of MRD response.
- Progression-free survival (PFS)

5.1.2 Assessment of Efficacy

5.1.2.1 Laboratory parameters

The following laboratory parameters must be evaluated to assess response of treatment:

- Multiple myeloma (MM) cells in bone marrow
Analysis of myeloma cells in bone marrow will be conducted using a diagnostic FACS panel including markers for CD45, CD38, CD19, CD138, CD56 and kappa/lambda chains. Scheduled sampling time points will be as follows (see [flow charts](#)): within 14 days before day 1 cycle 1 or in cycle 1, day 1 before start of treatment, when M protein/FLC becomes undetectable during treatment, on day 29 of cycle 3 and at EOT. **The analysis will be performed centrally. Percentage (%) of plasma cells in bone marrow should be assessed locally according to institutional standards and documented in eCRF at each timepoint.**
- M protein will be measured in serum at the beginning and at the end of each treatment period, i.e. at baseline (screening or Cycle 1 Day 1) and at Cycle 1 Day 29, Cycle 2 Day 1 and Cycle 2 Day 29 and Cycle X Day 1, Cycle X Day 29 and at EOT. M protein measurements in urine will only be followed up if positive for M protein in serum at

Proprietary confidential information.

© 2018 Boehringer Ingelheim International GmbH or one or more of its affiliated companies. All rights reserved.

This document may not - in full or in part - be passed on, reproduced, published or otherwise used without prior written permission.

baseline (Cycle 1 Day 1). Time points for urine analysis for M protein will be the same as for serum. **Measurements will be performed locally.**

- Free Light Chains (FLC)
In case of free kappa/lambda light chain (FLC) multiple myeloma (M protein negative cases) FLC will be analysed in serum and urine at the same time points as for M protein described above. Measurements will be performed locally. Levels of involved/uninvolved FLC, ratio of monoclonal lambda FLC / kappa FLC and ratio of monoclonal kappa FLC /lambda FLC will be determined. **Measurements will be performed locally.**
- The analysis of immunoglobulins (IgG, IgA, IgM) will be performed at baseline, followed by intervals of two weeks and at EOT. **Measurements will be performed locally.**
- β 2-microglobulin will be measured in serum as recommended for M protein described above. In urine, measurements will be done at baseline and every 6 weeks and at EOT. **Measurements will be performed locally.**
- Total calcium levels will be investigated at baseline, before start of treatment and at the end of each treatment cycle, i.e.: Cycle X Day 1, Cycle X day 29 and EOT. **Measurements will be performed locally.**

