3.3.2 Inclusion criteria

1. Patients with a documented diagnosis of relapsed and/or refractory multiple myeloma who progressed after at least two prior treatment regimens, including both a proteasome inhibitor as well as an immune - modulatory drug at time of screening
2. Must have measurable disease, defined by one or more of following at time of screening:
 - a serum M protein > 0.5 g/dl measured by serum protein electrophoresis
 - urinary M protein excretion > 200 mg/24 hours
 - serum free light chain (FLC) measurement > 10 mg/dl, provided that the serum FLC ratio is abnormal
3. Relapse or progression of disease with an indication for therapy as per investigator`s judgment at time of screening
4. Life expectancy of at least 6 months as per investigator`s judgment at time of screening
5. ECOG Performance Status 0, 1 or 2 at time of screening
6. Age \geq 18 years at time of screening
7. Written informed consent which is consistent with ICH-GCP guidelines and local legislation.
8. Able to adhere to the study visit schedule e.g. ability to come to the clinic and adhere to other protocol requirements
9. Indwelling central venous catheter or willingness to undergo intra venous central line placement

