5.1.2.2 Objective response rate

Objective response rate is defined as the percentage of patients achieving a sCR, CR, PR and VGPR and will be evaluated according to the response criteria of the International Myeloma Working Group (IMWG, 2006; [Appendix 10.1](#)).

- Stringent complete response (sCR)
CR as defined below plus normal FLC ratio and absence of clonal cells in bone marrow by immunohistochemistry or immunofluorescence.
- Complete response (CR)
Complete response is defined as negative immunofixation on the serum and urine and disappearance of any soft tissue plasmacytomas and < 5% plasma cells in bone marrow.
- Very good partial response (VGPR)
Serum and urine M-protein detectable by immunofixation but not on electrophoresis or > 90% reduction in serum M-protein plus urine M-protein level < 100 mg/24 h.
- Partial response (PR)
Partial response is defined as a > 50% reduction of serum M-protein and reduction in 24 hours urinary M-protein by >90% or to < 200 mg/24 h.

Proprietary confidential information.

© 2018 Boehringer Ingelheim International GmbH or one or more of its affiliated companies. All rights reserved.

This document may not - in full or in part - be passed on, reproduced, published or otherwise used without prior written permission.

If the serum and urine M-protein are unmeasurable a > 50% decrease in the difference between involved and uninvolved FLC levels is required in place of the M-protein criteria.

If serum and urine M-protein are not measurable, and serum free light assay is also not measurable, a > 50% reduction in plasma cells is required in place of M-protein, provided baseline bone marrow plasma cell percentage was > 30%.

In addition to the above listed criteria, if present at baseline, a > 50% reduction in the size of soft tissue plasmacytomas is also required.

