5.1.2.6 Progression

Progression is defined as an increase of > 25% from lowest response value in any one or more of the following:

- Serum M-component and/or (the absolute increase must be > 0.5 g/dL)
- Urine M-component and/or (the absolute increase must be > 200 mg/24 h)

Only in patients without measurable serum and urine M-protein levels; the difference between involved and uninvolved FLC levels. The absolute increase must be > 10 mg/dL

- Bone marrow plasma cell percentage; the absolute percentage must be > 10%
- Definite development of new bone lesions or soft tissue plasmacytomas or definite increase in the size of existing bone lesions or soft tissue plasmacytomas
- Development of hypercalcaemia (corrected serum calcium > 11.5 mg/dL or 2.65 mmol/L) that can be attributed solely to the plasma cell proliferative disorder

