10. APPENDICES

10.1 INTERNATIONAL MYELOMA WORKING GROUP (IMWG) UNIFORM RESPONSE CRITERIA FOR MULTIPLE MYELOMA

| Response | IMWG criteria ¹ |
|----------------------------------|---|
| sCR | CR as defined below plus normal FLC ratio and absence of clonal cells in bone marrow ² by immunohistochemistry or immunofluorescence ³ |
| CR | Negative immunofixation on the serum and urine and disappearance of any soft tissue plasmacytomas and < 5% plasma cells in bone marrow ³ |
| VGPR | Serum and urine M-protein detectable by immunofixation but not on electrophoresis or > 90% reduction in serum M-protein plus urine M-protein level < 100 mg/24 h |
| PR | > 50% reduction of serum M-protein and reduction in 24 hours urinary M-protein by >90% or to < 200 mg/24 h If the serum and urine M-protein are unmeasurable, ⁵ a > 50% decrease in the difference between involved and uninvolved FLC levels is required in place of the M-protein criteria If serum and urine M-protein are not measurable, and serum free light assay is also not measurable, > 50% reduction in plasma cells is required in place of M-protein, provided baseline bone marrow plasma cell percentage was > 30% In addition to the above listed criteria, if present at baseline, a > 50% reduction in the size of soft tissue plasmacytomas is also required |
| SD | Not meeting criteria for CR, VGPR, PR, or progressive disease |
| Progressive disease ⁴ | Increase of > 25% from lowest response value in any one or more of the following: Serum M-component and/or (the absolute increase must be > 0.5 g/dL) ⁵ Urine M-component and/or (the absolute increase must be > 200 mg/24 h) Only in patients without measurable serum and urine M-protein levels; the difference between involved and uninvolved FLC levels. The absolute increase must be > 10 mg/dL Bone marrow plasma cell percentage; the absolute percentage must be > 10% ⁶ Definite development of new bone lesions or soft tissue plasmacytomas or definite increase in the size of existing bone lesions or soft tissue plasmacytomas Development of hypercalcaemia (corrected serum calcium > 11.5 mg/dL or 2.65 mmol/L) that can be attributed solely to the plasma cell proliferative disorder |

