| Relapse | Clinical relapse requires one or more of: Direct indicators of increasing disease and/or end organ dysfunction (CRAB features) ⁵ . It is not used in calculation of time to progression or progression-free survival but is listed here as something that can be reported optionally or for use in clinical practice Development of new soft tissue plasmacytomas or bone lesions |

Proprietary confidential information.

© 2018 Boehringer Ingelheim International GmbH or one or more of its affiliated companies. All rights reserved.

This document may not - in full or in part - be passed on, reproduced, published or otherwise used without prior written permission.

| | |
|---|--|
| | Definite increase in the size of existing plasmacytomas or bone lesions. A definite increase is defined as a 50% (and at least 1 cm) increase as measured serially by the sum of the products of the cross-diameters of the measurable lesion Hypercalcemia (> 11.5 mg/dL) [2.65 mmol/L] Decrease in haemoglobin of > 2 g/dL [1.25 mmol/L] Rise in serum creatinine by 2 mg/dL or more [177 mmol/L or more] |
| Relapse from CR5 (To be used only if the end point studied is DFS) ⁷ | Any one or more of the following: Reappearance of serum or urine M-protein by immunofixation or electrophoresis Development of > 5% plasma cells in the bone marrow ⁶ Appearance of any other sign of progression (i.e., new plasmacytoma, lytic bone lesion, or hypercalcaemia) |

¹Adapted from Durie BGM, et al. Leukemia 2006; 20: 1467-1473 ([R14-4478](#)); and Kyle RA, Rajkumar SV. Leukemia 2009; 23:3-9 ([R15-0269](#)).

Note: A clarification to IMWG criteria for coding CR and VGPR in patients in whom the only measurable disease is by serum FLC levels: CR in such patients is defined as a normal FLC ratio of 0.26–1.65 in addition to CR criteria listed above. VGPR in such patients is defined as a >90% decrease in the difference between involved and uninvolved free light chain (FLC) levels.

² Confirmation with repeat bone marrow biopsy not needed.

³ Presence/absence of clonal cells is based upon the kappa/lambda ratio. An abnormal kappa/lambda ratio by immunohistochemistry and/or immunofluorescence requires a minimum of 100 plasma cells for analysis. An abnormal ratio reflecting presence of an abnormal clone is kappa/lambda of > 4:1 or < 1:2.

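### Protocol 5.1.2.1 follows urine M-protein only in patients with serum M-protein at baseline, but inclusion criterion 2 admits patients on urine M-protein alone (minor)

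*Protocol*

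**What the plan says.** **Entry.** Protocol 3.3.2, criterion 2, asks for at least one of three markers at screening. One of them, sufficient by itself, is "urinary M protein excretion > 200 mg/24 hours". The others are serum M-protein above 0.5 g/dl, and serum FLC above 10 mg/dl with an abnormal ratio.

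**Sampling.** Protocol 5.1.2.1 measures serum M-protein at the start and end of each treatment period and at EOT. For urine the rule is "M protein measurements in urine will only be followed up if positive for M protein in serum" at baseline; where urine is followed, it shares the serum time points. A separate bullet gives serum and urine FLC at those times to M-protein-negative light chain cases.

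**Response (Protocol 5.1.2.2, Appendix 10.1).**
- CR: "Negative immunofixation on the serum and urine and disappearance of any soft tissue plasmacytomas", plus a marrow condition. sCR is CR with further conditions.
- VGPR: "Serum and urine M-protein detectable by immunofixation but not on electrophoresis or > 90% reduction in serum M-protein", the second branch also needing urine M-protein below 100 mg/24 h.
- PR: "Partial response is defined as a > 50% reduction of serum M-protein and reduction in 24 hours urinary M-protein by >90"%, or a fall in urine to below 200 mg/24 h.

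**Progression.** Protocol 5.1.2.6 requires an increase of more than 25% "from lowest response value in any one or more of the following"; the urine M-component is one of those listed.

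**Analysis.** SAP 7.5.2 takes response as assessed by the investigator under IMWG criteria, with exact Clopper-Pearson intervals for ORR. SAP 6.3 uses the treated set for efficacy. Protocol 7.5 imputes no missing efficacy data.

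**The concern.** A patient can qualify on a marker that the sampling rule then stops following. If that patient responds, the urine result needed to record the response is not scheduled. The patient nevertheless stays in the treated-set denominator, so the cohort's ORR falls and a DOR record is lost. If the patient progresses by urine, no scheduled test looks for it, so PFS may be lengthened. The response-triggered marrow and MRD sample (flow chart footnotes 8 and 9) is taken when M-protein or FLC becomes undetectable. In this patient that trigger would rest on FLC alone, if FLC is done at all.

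**Working it through.** The plan has no figure to reproduce here: Protocol 7.7 says the sample size has no power calculation. The check is mainly a comparison of sections.

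**1. Who is affected.** The condition in 5.1.2.1 is positivity in serum, not measurability.

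| Serum M-protein at baseline | Urine M-protein > 200 mg/24 h | Urine followed under 5.1.2.1? |
|---|---|---|
| Above 0.5 g/dl | Yes | Yes |
| Detectable, at or below 0.5 g/dl | Yes | Yes |
| Negative | Yes | No |

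Only the last row is affected.

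**2. Does response need urine?** CR needs urine immunofixation and sCR inherits that. Both VGPR branches use urine, as does the M-protein route to PR.

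**3. Do the substitutes apply?** No.
- FLC for PR: "If the serum and urine M-protein are unmeasurable a > 50% decrease in the difference between involved and uninvolved FLC levels is required". This patient's urine M-protein is measurable.
- Plasma cells for PR: serum M-protein, urine M-protein and FLC must all be unmeasurable.
- Appendix 10.1 note on CR and VGPR: it applies "in patients in whom the only measurable disease is by serum FLC levels".
- FLC criterion for progression (5.1.2.6): confined to patients without measurable serum and urine M-protein.

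So even if a site treats the patient as M-protein-negative and measures FLC, the criteria do not accept FLC in place of urine M-protein. The safety-laboratory urine protein (5.2.4.1) is a semiquantitative dipstick and meets none of the criteria.

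**4. What is still observed.** Serum M-protein is measured in every patient. Calcium is scheduled on days 1 and 29 of each cycle and at EOT, clinical disease status at each cycle start and EOT, and MRI every other cycle. Marrow is sampled at day 29 of cycle 3 and at EOT. The non-urine routes to progression and the fixed MRD samples therefore remain.

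**5. Size of one unscored responder.** The ORR shift is 1/n: 1/3 = 33.3 points and 1/6 = 16.7 points. The exact 95% limits for x responders among n are the 0.025 quantile of Beta(x, n−x+1) and the 0.975 quantile of Beta(x+1, n−x).

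| n | Response recorded | Same patient unscored |
|---|---|---|
| 3 | 2/3 = 66.7% (9.4 to 99.2) | 1/3 = 33.3% (0.8 to 90.6) |
| 6 | 3/6 = 50.0% (11.8 to 88.2) | 2/6 = 33.3% (4.3 to 77.7) |

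For n = 3 the limits can be checked by hand. The upper limit for 2/3 is 0.975^(1/3) = 0.992. Its lower limit solves 3p² − 2p³ = 0.025, giving p = 0.094. By symmetry the limits for 1/3 are 0.008 and 0.906. In both cohort sizes the shifted estimate lies well inside the first interval.

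**6. Extra samples under the fix.** Post-baseline serum time points over five cycles: day 29 of cycles 1 to 5 (5), day 1 of cycles 2 to 5 (4) and EOT (1), so 5 + 4 + 1 = 10.

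**The case against.** **The schedule cannot be seen in full.** Protocol 5.1.1 refers efficacy assessments to the flow charts, and 6.2.2 refers blood and urine biomarkers to a specific flow chart that is not shown. Section 3.1.1 cites 5.1.2 among the sections covering specific biomarkers. The visit tables for cycle 1 visit 1 and for visits 1 to 4 of later cycles list blood and urine markers with no serum condition. If these schedule urine M-protein for everyone, the samples exist and only the restriction in 5.1.2.1 is wrong. If they mean another marker, such as urine β2-microglobulin, the gap stands. Either way the text needs reconciling, but this limits how firmly the consequence can be stated.

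**Investigators may test anyway.** Measurements are local, nothing forbids unscheduled urine testing, and the IMWG criteria themselves call for it. This stands. What remains is that scoring would then depend on site practice.

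**A stronger reading.** A reader might infer that such a patient can never be scored as a responder, or that changing the sampling sentence would make every category reachable. The documents support neither. The first ignores the unseen flow chart and unscheduled testing. The second fails on three counts: 5.1.2.1 does not name urine immunofixation (needed for CR), it schedules FLC only in M-protein-negative cases (sCR needs a normal ratio), and PR and VGPR carry serum requirements that a serum-negative patient cannot meet as written. That last problem is not caused by the sampling rule and is a separate question.

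**Conclusion.** The mismatch is real: the sampling rule in 5.1.2.1 omits a marker that criterion 2 accepts as the sole measurable disease. The severity is minor. The documents give no frequency for serum-negative, urine-measurable patients. The ORR shifts in the working assume that one such patient is enrolled, truly responds, and has no urine result from another schedule or from the investigator. PFS may be lengthened rather than lost, because the other routes to progression are still assessed. All the endpoints touched are secondary and descriptive, with no formal tests (Protocol 7.2); MTD, DLT and dose escalation are unaffected.

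**What to change.** In 5.1.2.1, extend the condition so that urine M-protein is followed when M-protein is positive in serum or in urine at baseline. Then reconcile that sentence with Tables 6.2.4.1: 1, 6.2.4.2: 1 and 6.2.4.2: 2 and with the separate biomarker flow chart, so that all give the same urine schedule.

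The cost is a wording change plus local 24-hour urine M-protein at the serum time points, up to 10 post-baseline over five cycles, in the few serum-negative, urine-positive patients. The urine already taken for β2-microglobulin does not cover this: after baseline it is six-weekly with a sample at EOT, and it is not described as a 24-hour collection.

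Separately, and not part of this change, the sponsor should state how PR and VGPR are scored in a patient with no serum M-protein. That would alter adopted response criteria and needs its own thought. For example, if the alternative of urine below 200 mg/24 h could stand alone, a patient entering at 220 mg/24 h would reach PR at 199, a fall of (220 − 199)/220 = 9.5%.
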